12. ANALYSIS OF SAFETY DATA

All safety evaluations will be performed using each safety analysis set unless specified otherwise.

As the nDNA-PMM subjects will only be recruited from a subset of the REN001-202 sites, summaries may also be presented only including mtDNA-PMM subjects from the same sites. Two separate sets of subjects may be used: the subjects who received mavodelpar in REN001-201 with their data from the start of REN001-201, and the subjects who received placebo in REN001-201 from the start of REN001-202. Consideration will be given to the duration of exposure for nDNA-PMM subjects when summarising the data from the mtDNA-PMM subjects (e.g., if the duration of exposure of nDNA-PMM subjects is up to 6 months, only the first 6 months of data for the mtDNA-PMM subjects will be used).

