Physician-PMM phenotypic description				X		X			X	X	X
Physical exam ³ (inc. weight)			X	X	X	X	X	X	X	X	X
ECG			X	X	X	X	X	X	X	X	X
Vital signs		X	X	X	X	X	X	X	X	X	X
Safety bloods haematology/biochemistry		X	X	X	X	X	X	X	X	X	X
HbA1c						X			X	X	X
Blood for bone and calcium markers				X		X		X	X	X	X
PK blood sample for REN001 ⁴		X	X	X	X	X	X	X	X	X	X
Urinalysis inc. pregnancy testing ⁵		X	X	X	X	X	X	X	X	X	X
Urine drugs of abuse		X	X	X	X	X	X	X	X	X	X
Serum FSH ⁶		X ⁷	X	X	X	X	X	X	X	X	X
Urine NTX bone markers		X	X	X	X	X	X	X	X	X	X
PROs ⁸		X	X	X	X	X	X	X	X	X	X
12MWT			X	X	X	X	X	X	X	X	X
Eye examination			X	X	X	X	X	X	X	X	X
DXA Scan ⁹									X	X	X
Dispense Study Drug			X	X		X		X	X	X	
Concomitant medication review	X										X
AE review	X										X
Dosing of study drug	X		X	X	X	X	X	X	X	X	X

¹ See Table 2. It is expected that most subjects will enrol at the STRIDE Week 24 visit with the baseline visit for this study coinciding with the STRIDE Week 24 visit. With additional assessments subjects can also enrol at the STRIDE FU visit, or at any time after exiting Study REN001-101 or STRIDE, and nDNA-PMM subjects (Table 2 and Section 6.1).

² If subject discontinues study drug, they will be required to attend an early withdrawal visit as soon as possible after their last dose of study drug. A FU telephone call by the site approx. 30 (±7) days after last dose of study drug is required unless subject transfers to commercially available mavodelpar. Clinically significant abnormalities should be followed up until resolved/stabilized.

³ Brief symptom directed physical exam can be done post baseline.

⁴ PK samples (1 or 2) will be collected at all visits except Month 3 when 4 PK samples will be collected at 0,1,2,4 hrs post dose.

⁵ Urine home pregnancy test kits will be supplied to WOCCBP to enable monthly pregnancy testing. The study centre must contact the subject to confirm the pregnancy test results. The final test will be performed prior to the follow-up telephone contact approximately 30 days after the last dose of study drug.

⁶ FSH test should be done during study if menopausal symptoms develop.

⁷ FSH to be measured for all females (aged ≥45 years) not confirmed as post-menopausal.

⁸ PROs include MFIS, PGIS and PGIC (muscle and fatigue symptoms), SF-36, PROMIS, WPAI:SHP, BPI. BPI will be carried out at Month 12 and Month 24 only. After the M24 visit, only the PGIS will be conducted at each visit. The PGIC will be carried out at Month 12, 24, 36 and 48 only.

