2. INTRODUCTION

[figure not shown]
This Statistical Analysis Plan (SAP) details the statistical analyses for the REN001-202 Open Label study. REN001-202 is an open label long term (48 months) safety study in subjects with Primary Mitochondrial Myopathy (PMM) due to mitochondrial DNA mutations (mtDNA-PMM) or nuclear DNA mutations (nDNA-PMM). Subjects with mtDNA-PMM will have previously completed treatment in Study REN001-201 or participated in Study REN001-101. Subjects with nDNA-PMM who enrol in this study will be mavodelpar (REN001) naïve. As this study is an open label extension study to REN001-201 the two studies will be reported together for the REN001-202 clinical study report (CSR). Therefore, this SAP also details the planned integrated analysis for these two studies from a safety perspective and, the planned analysis will provide long term safety data of up to 54 months exposure to mavodelpar for mtDNA subjects who receive mavodelpar in REN001-201.

Figure 1 below shows the different pathways a subject can enter REN001-202 and the 5 distinct reporting groups. These groups provide the following assessments for mavodelpar 100mg once daily:

- Long-term safety data
- Long-term tolerability
- Bridging data (safety and efficacy) between nDNA-PMM subjects and mtDNA subjects

While efficacy data will be presented, these should be interpreted in a descriptive manner since the design of this open label study, does not enable obtaining either reliable or fully interpretable confirmatory evidence of efficacy, including 'durability of effect'. These limitations regarding long-term efficacy assessments are due to several key issues: the lack of a randomized comparator group, the lack of blinding when assessing effects on effort-dependent outcome measures, and the potential impact of meaningfully informative missing data.

Figure 1 Subject Reporting Groups

The data will be presented in different ways:

- from the start of REN001-202. These data presentations will focus on all 5 reporting groups and only consider data collected in REN001-202. This will allow the assessment of mtDNA-PMM and nDNA-PMM over 48 months of mavodelpar treatment. It will also provide an assessment of:
 - the continued safety of mavodelpar for subjects who received mavodelpar for 6 months in REN001-201;
 - the introduction of mavodelpar for subjects who received placebo for 6 months in REN001-201;

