After the baseline visit, subjects will have study visits at Months 1, 3, 6, 12, 18, 24, 30, 36, 42 and 48 (subjects at the German sites will also have visits at Month 9 and 15) from the start of REN001-202. At a final follow up there will be a telephone call from the study centre to the subject approximately 30 days after the last dose of study drug. A final follow-up telephone call will not be required if mavodelpar has been approved within the country and the subject switches to commercially available medication. The schedule of assessments for REN001-202 is detailed in [Section 3.4](#) and the REN001-201 schedule of assessments is included in [Appendix 2](#).

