Subjects who satisfy the criteria for values of potential clinical importance (PCI), identified in the table below, will be summarized and listed. The summary will present the number of subjects with at least one on-treatment post baseline value (including unscheduled visits) satisfying the criteria. The listing will have a similar layout to the overall laboratory listing but will only include those subjects who satisfy the criteria for a specific parameter. The records satisfying the criteria will be identified on the listing. The criteria are:

Category	Parameter	Criteria
Chemistry	Creatine kinase (CK)	Normal baseline value and post $\geq 5 \times$ ULN > ULN baseline value and post $\geq 5 \times$ baseline level
	Aldolase	Normal baseline value and post > ULN
	Troponin I	> ULN
	Potential Hy's Law (ALT, AST, total bilirubin and alkaline phosphatase)	ALT or AST > 3 x ULN and Total bilirubin > 2 x ULN and Alkaline Phosphatase $\leq 2 \times$ ULN

An evaluation of Drug-Induced Serious Hepatotoxicity (eDISH) plot will be generated. The plot will include all post baseline data and will present ALT relative to the upper limit of normal (ULN) on the x-axis and total bilirubin relative to the ULN on the y-axis using a log scale for both axes. Reference lines for Hy's law thresholds, i.e., ALT = 3 x ULN and total bilirubin = 2 x ULN, will be added. The plot will identify group and mutational group and separate plots will be done for on-treatment and off-treatment records.

A spaghetti plot for the changes from baseline in creatine kinase (CK) over time will be presented. The actual sampling day will be used on the x-axis (baseline will be set to day 1). A solid line will be used to connect measurements; however, if the measurement was collected after the last dose of study drug plus one day, then a dotted line will be used. Group will be identified on the plot. The plot will be repeated for aldolase and troponin I. Individual CK, aldolase, ALT, AST and troponin I values relative to the ULN will be plotted over time (i.e., one plot per subject) and group and mutation type will be identified.

The actual sampling day will be used on the x-axis (baseline will be set to day 1). The day of last dose of study drug will be identified on the plot with a vertical reference line.

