APPENDIX 2 – REN001-201 SCHEDULE OF ASSESSMENTS

Time and Events Table	Screening	Baseline ^{1,2} (Day 1)	Week 2 ³ (Day 14)	Week 4 ³ (Day 28)	Week 8 (Day 56)	Week 12 ^{2,4} (Day 84)	Week 16 (Day 112)	Week 18 ³ (Day 126)	Week 20 (Day 140)	Week 24 ^{2,4} (Day 168)	Early Termn ^{2,5}	Follow Up ³ (21-28 days post last dose)
Visit number	1	2	3	4	5	6	7	8				
Window (days)			±3	±3	±7	±7						
Informed Consent ²⁰	X											
Completion of Proforma and data entered into eCRF ⁶	X											
Demographics	X											
Medical/medication/drug/alcohol/tobacco history ⁷	X											
Physician completion of PMM phenotypic description		X								X	X	
Physical exam ⁸	X	X				X				X	X	
12-lead ECG	X	X				X				X	X	
Supine Vital signs (BP, PR and temperature)	X	X	X	X				X		X	X	X
Serum FSH ⁹	X											
HbA1c	X									X	X	
Hepatitis B/C/HIV	X											
Safety labs (inc. urinalysis)	X	X ¹⁰	X	X		X		X		X ¹¹	X	X ¹¹
Blood sample for bone and calcium markers		X				X				X	X	
Pregnancy Test (WOCBP only) ¹²	X	X		X	X	X	X		X	X	X	X
Blood sample for genotyping ¹³	X											
Population PK blood sample ¹⁴		X	X	X		X		X		X	X	
Urine drugs of abuse	X	X				X				X	X	

Time and Events Table	Screening	Baseline ^{1,2} (Day 1)	Week 2 ³ (Day 14)	Week 4 ³ (Day 28)	Week 8 (Day 56)	Week 12 ^{2,4} (Day 84)	Week 16 (Day 112)	Week 18 ³ (Day 126)	Week 20 (Day 140)	Week 24 ^{2,4} (Day 168)	Early Term ^{2,5}	Follow Up ³ (21-28 days post last dose)
Urine NTX		X				X				X	X	
Sites to provide appropriate snacks and lunch	X	X				X				X	X	
Pedometer eDiary data collection (inc. review)	X	X ¹⁵	X			X		X		X		
MFIS / PGIS (muscle symptoms), PGIS (fatigue symptoms) and PROMIS – Short form FACIT fatigue 13a	X	X	X			X		X		X	X	
SF-36 / BPI and WPAI:SHP		X	X			X		X		X	X	
PGIC (muscle symptoms) and PGIC (fatigue symptoms)										X	X	
12 Minute Walk Test	X ¹⁶	X				X				X	X	
30STS		X				X				X	X	
IMP Capsule Counts			X	X		X		X		X	X	
Eye examination	X ¹⁷					X				X	X	
Wrist radiograph	X ¹⁸											
DXA Scan (REN001-201-DXA sub-study) ²¹	X									X	X	
Concomitant medication review	X											X
Dosing		X ¹⁹									X	
AE collection and reporting	X											X

1. Screening visit must take place a maximum of 8 weeks before the Baseline visit.
2. If appropriate and feasible Baseline, Week 12, Week 24 /Early Termination visits may be conducted over 2 days at the Investigators discretion.
3. In countries where the regulatory body allows, visit may be in the Study Center or a home nursing visit.

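### In one optional same-site bridging set, mtDNA subjects have 5 scheduled safety-lab draws in 6 months against 3 for nDNA subjects, so laboratory PCI percentages differ by schedule alone

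*SAP*

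**What the plan says.** SAP section 2 lists among the uses of the reporting groups "Bridging data (safety and efficacy) between nDNA-PMM subjects and mtDNA subjects". SAP section 12 adds that, because nDNA-PMM subjects come from only some sites, summaries restricted to mtDNA-PMM subjects at those same sites may be produced. It names two possible mtDNA sets. The first is "the subjects who received mavodelpar in REN001-201 with their data from the start of REN001-201". The second, which follows the REN001-202 visit schedule, is "the subjects who received placebo in REN001-201 from the start of REN001-202". Alignment is by exposure. The example given is that "if the duration of exposure of nDNA-PMM subjects is up to 6 months, only the first 6 months of data for the mtDNA-PMM subjects will" enter the summaries.

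For the laboratory PCI criteria (CK, aldolase, troponin I and potential Hy's Law), SAP section 12.2 states: "The summary will present the number of subjects with at least one on-treatment post baseline value (including unscheduled visits) satisfying the criteria".

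The two studies have different laboratory schedules. In SAP Appendix 2, the STRIDE (REN001-201) row beginning "Safety labs (inc. urinalysis" is marked at Weeks 2, 4, 12, 18 and 24 after baseline. In REN001-202, "subjects will have study visits at Months 1, 3, 6, 12, 18, 24, 30, 36, 42 and 48" (SAP section 3.3), and the row "Safety bloods haematology/biochemistry" in Protocol Table 3 is marked at each of them. Protocol sections 6.2 to 6.4 confirm haematology and biochemistry at Months 1, 3 and 6.

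SAP section 8.2 leaves some visits that only STRIDE mavodelpar subjects have, including Weeks 2 and 18, out of the by-visit summaries from the start of REN001 treatment. It does not mention the PCI counts.

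**The concern.** A count of subjects with at least one qualifying value depends on how often they are tested as well as on their risk. Equal exposure time does not mean equal opportunity to be counted. If two groups have the same true risk and one is tested five times and the other three, the first will tend to show the higher percentage.

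Here the denser schedule is in the mtDNA set, so the distortion favours the nDNA group. Protocol section 1.5 says there is no prior REN001 exposure in nDNA patients and that their safety profile is not expected to differ significantly. Protocol section 1.3 says the data will support further development in this population. A difference toward reassurance could partly hide a real nDNA excess. CK is the analyte where this is most plausible, because Protocol sections 1.4.2.1 and 3.7.1 describe CK rises in PMM as often transient. Draws weeks apart can then catch separate episodes.

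**Working it through.** **Check against the plan's own figure.** The REN001-202 post-baseline visits (Months 1, 3, 6, 12, 18, 24, 30, 36, 42, 48) number 10. Protocol Table 5 gives 10 biochemistry samples after baseline over 48 months, so the visit count is reproduced.

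**Scheduled draws since first mavodelpar dose** (non-German sites; STRIDE mavodelpar subjects who roll over at Week 24):

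| Up to | STRIDE-based mtDNA set | nDNA |
|---|---|---|
| Day 168 | Days 14, 28, 84, 126, 168 = 5 | Days 28, 84, 168 = 3 |
| Day 336 | the 5 above, plus 168+28, 168+84, 168+168 = 8 | the 3 above, plus Day 336 = 4 |

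The extra German visits (Months 9 and 15) fall after Day 168 and do not change the first row. The second mtDNA set (placebo in STRIDE, then REN001-202) has the nDNA schedule: 3 against 3.

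**Size.** The documents give no per-draw PCI rate. I assume p = 2%, 5% and 10%, the same in both groups.

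For independent draws, P(at least one in k) = 1 − (1 − p)^k. At p = 5%: 1 − 0.95^5 = 22.6% and 1 − 0.95^3 = 14.3%.

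For within-subject correlation ρ, I use a beta-binomial with a = p(1 − ρ)/ρ and b = (1 − p)(1 − ρ)/ρ, so P = 1 − Π (b + j)/(a + b + j) for j = 0 to k − 1. At ρ = 0.5 and p = 5%, a = 0.05 and b = 0.95. For k = 3, P = 1 − (0.95/1)(1.95/2)(2.95/3) = 8.9%. Multiplying the product by (3.95/4)(4.95/5) gives 11.0% for k = 5.

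| p | ρ = 0: 5 vs 3 draws | Ratio | ρ = 0.5: 5 vs 3 draws | Ratio |
|---|---|---|---|---|
| 2% | 9.6% vs 5.9% | 1.63 | 4.5% vs 3.6% | 1.24 |
| 5% | 22.6% vs 14.3% | 1.59 | 11.0% vs 8.9% | 1.23 |
| 10% | 41.0% vs 27.1% | 1.51 | 21.0% vs 17.3% | 1.21 |

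At Day 336 (8 vs 4 draws) and p = 5%, the figures are 33.7% vs 18.5% if independent and 12.9% vs 10.1% at ρ = 0.5.

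**After restricting to common visits.** Keeping Week 4/Month 1, Week 12/Month 3 and Week 24/Month 6 gives 3 vs 3 by Day 168. Adding Month 12 gives 4 vs 4 by Day 336. The schedule effect on scheduled values is then removed.

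**The case against.** The strongest reply is about scope. The same-site summaries are optional and descriptive, no testing is planned (SAP section 8.1), and only one of the two sets is affected. A reader might infer that the nDNA-to-mtDNA safety bridging as a whole is distorted. The documents do not support that. The planned display from the start of REN001-202 (SAP section 8.2) uses only REN001-202 data, so both mutation groups follow the same scheduled visits, and the placebo-to-REN001 group is shown separately. This part of the objection stands in full.

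Second, counting every value looks deliberate. SAP section 6 keeps the German Month 9 and 15 values out of by-visit tables but lets them feed the PCI summaries, and section 12.2 includes unscheduled values. Catching every signal is a good reason to keep the all-values count. It does not make two such counts comparable when the schedules differ.

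Third, the size is assumed. A ratio of 1.5 to 1.6 might be read as the expected inflation, but it needs independent draws within a subject and is an upper bound. At correlation 0.5 and p = 5%, the gap is about 1 subject per 50 (50 × (11.0% − 8.9%)), and nDNA enrolment is at most 50. The assumed rates should not be carried over to Hy's Law: nothing in the documents supports 2% to 10% per draw for that criterion, and at a near-zero rate the gap would be negligible. Appendix 2 also does not itemise the STRIDE panel by visit. These limits stand on size but leave the direction unchanged where the analytes were measured.

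A reader might also extend the argument to adverse-event counts, because STRIDE has more visits. That is not shown. Protocol section 7.1.1.8.2 lets subjects report events at any time, and no such effect is quantified here. Nor does the point extend to QTcF at 6 months: both schedules have two post-baseline ECGs by then (Weeks 12 and 24; Months 3 and 6).

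**Conclusion.** The point holds for laboratory PCI percentages in the STRIDE-based mtDNA set of the optional same-site summaries, and only there. Scheduled draws are 5 vs 3 by Day 168, and 8 vs 4 by Day 336 for Week 24 rollovers at non-German sites. SAP section 12 aligns exposure time only, and the Week 2 and Week 18 exclusion in section 8.2 covers by-visit tables only. The mtDNA percentage is therefore raised by schedule alone, unless abnormal values are fully persistent within a subject.

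Under assumed per-draw rates of 2% to 10%, the 6-month ratio lies between about 1.2 (correlation 0.5) and 1.5 to 1.6 (independence, the upper bound). This rests on equal true risk in the two groups and on the PCI analytes being measured at every STRIDE safety-lab draw. No error rate or power is affected. It is a modest interpretive bias that is cheap to remove.

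**What to change.** In SAP section 12, with a cross-reference from 12.2, specify that if the STRIDE-based mtDNA set is presented, the laboratory PCI table will carry two rows per criterion:

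- **Like-for-like row:** for both groups, only values from scheduled visits common to both timelines, counted from first mavodelpar dose. These are Months 1, 3 and 6, then the six-monthly visits from Month 12 where exposure is longer.
- **All-values row:** the count as now defined in section 12.2, including unscheduled values.

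State the number of scheduled draws per set in the table header or a footnote.

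The cost is a few lines of SAP text before database lock and one filter in the PCI program. SAP section 8.4 already gives both studies the same analysis windows for the first three common visits (Days 21–35, 63–105 and 147–189). The downside is that the like-for-like row omits some STRIDE values and unscheduled repeats, including repeat liver tests prompted by Protocol section 3.7.2. They stay in the all-values row, which is why that row must be kept.

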3.3. STUDY DESIGN

REN001-202 is a global Phase 2b open label long-term safety study initially set up for mtDNA-PMM subjects who complete treatment in REN001-201 or who were participating in REN001-101 (a UK only study) when it was ended due to the COVID-19 pandemic. Subjects will receive mavodelpar 100 mg once daily for 48 months.

Protocol Version 2.0 extended recruitment to subjects with nDNA-PMM and increased the predicted sample size. These subjects will enter the study naïve to mavodelpar.

Subjects enrolling from REN001-201 will be switching from taking blinded mavodelpar or placebo in the randomized controlled REN001-201 study to open label mavodelpar in REN001-202. At the time of enrolment into this long-term study, prior treatment allocation in REN001-201 will be unknown. Subjects who are nearing completion of their participation in REN001-201 will be invited to discuss continuing into this long-term safety study.

Hence, subjects may enter REN001-202 via the following pathway options:

1. At REN001-201 Week 24 (REN001-201 W24). Consequently, these subjects will not need to complete the REN001-201 FU visit.
2. At REN001-201 Follow-up (REN001-201 FU).
3. (a) After leaving REN001-201, following their completion of REN001-201 (REN001-201 Exit). This will result in a break in study participation where the subject is off study drug and not monitored in either study.
(b) After leaving study REN001-101. REN001-101 completed in March 2020 and therefore subjects will have not received mavodelpar for more than 2 years at the time of entry to REN001-202.
4. Recruitment of mavodelpar naïve nDNA-PMM subjects. A Patient Screening Oversight Committee (PSOC) will assess these subjects to confirm the medical diagnosis of nDNA-PMM prior to enrolment.

It is expected that most subjects transferring from REN001-201 will do so at the REN001-201 Week 24 visit to prevent an interruption in dosing and reduce the number of study visits and assessments. Their Week 24 REN001-201 visit will also be used as their Baseline visit for REN001-202.

Enrolment at the REN001-201 FU visit will require additional baseline assessments. Enrolment after exiting REN001-201, after participating in Study REN001-101 and for nDNA-PMM subjects, will require an additional screening visit to complete eligibility checks prior to enrolment. Note, all subjects enrolling from German sites will also need to satisfy additional eligibility checks irrespective of when they roll over from REN001-201.

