10. ANALYSIS OF EFFICACY DATA

All analyses will be based on the FAS for the groups from the start of REN001-202 and from the start of REN001-201 unless stated otherwise.

Missing data will be handled using the complete case methodology described in [Section 8.3.1](#).

As the nDNA-PMM subjects will only be recruited from a subset of the REN001-202 sites, summaries may also be presented only including mtDNA-PMM subjects from the same sites. Two separate sets of subjects may be used: the subjects who received mavodelpar in REN001-201 with their data from the start of REN001-201, and the subjects who received placebo in REN001-201 from the start of REN001-202. Consideration will be given to the duration of exposure for nDNA-PMM subjects when summarising the data from the mtDNA-PMM subjects (e.g., if the duration of exposure of nDNA-PMM subjects is up to 6 months, only the first 6 months of data for the mtDNA-PMM subjects will be used).

10.1. 12-MINUTE WALK TEST (12MWT)

Observed, change from baseline and percent change from baseline values will be summarized by visit using descriptive statistics. The associated 95% confidence intervals for the observed, change from baseline and percent change from baseline means will also be presented. The number of subjects withdrawn prior to the visit or with missing data will also be presented. Note missing data will include those subjects who prematurely stop the 12MWT and their reason for stopping is adjudicated as not being possibly related to the subject's PMM or study treatment.

Mean plots for observed, change from baseline and percent change from baseline values, with 95% confidence intervals will be presented by group with visit on the x-axis. A reference line for no change (i.e., $y=0$) will be included in the change from baseline and percent change from baseline plots.

Spaghetti plots for the changes from baseline will be plotted over time. The plots will be split by group. The y-axis will be uniform across the plots to allow comparisons. A reference line for no change (i.e., $y=0$) will be included.

The impact of the subgroups (specified in [Section 8.5](#)) on the 12MWD will also be investigated descriptively. Summaries will be presented by subgroup.

The number of stops and the number of falls will be summarized by visit. If a subject does not walk for the full 12 minutes, then this will be counted as an additional stop when summarizing.

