13. INTERIM ANALYSES

An interim synoptic CSR will be prepared for this study to be included in the regulatory submission package. The data cut will be the date of the last subject last visit in REN001-201 and the data will be extracted from the database after REN001-201 database has been locked. This CSR will include all REN001-202 data up to the data cut date and best efforts will be made to clean data up to this data cut date.

There will be a reduced set of safety outputs generated after submission for the 120-day safety update which is required as part of the submission package. The final CSR will occur after all subjects have had the ability to complete REN001-202, the data has been cleaned and the database locked.

An independently chaired Safety Review Committee (SRC) will review safety data at specified intervals for the duration of the study. The structure, function and operation of the SRC is detailed in the REN001-202 SRC charter. The SRC review of safety data will be limited to data from REN001-202 and will not be combined with REN001-201 data.

**14. CHANGES FROM PLANNED ANALYSES SPECIFIED
IN THE PROTOCOL**

None.

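### The optional nDNA-versus-mtDNA safety summaries match the groups on longest, not individual, follow-up, so at the interim cut crude nDNA event percentages would look too low against the REN001-201 mavodelpar subjects

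*SAP*

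**What the plan says.** SAP section 2 gives, as one purpose of the reporting groups, "Bridging data (safety and efficacy) between nDNA-PMM subjects and mtDNA subjects". SAP section 12 notes that nDNA subjects come from only some of the sites, and that "summaries may also be presented only including mtDNA-PMM subjects from the same sites". Two mtDNA sets may be used:

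- Set 1: "the subjects who received mavodelpar in REN001-201 with their data from the start of REN001-201".
- Set 2: "the subjects who received placebo in REN001-201 from the start of REN001-202".

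On follow-up, the text promises only that nDNA exposure will be considered, and gives one example: "if the duration of exposure of nDNA-PMM subjects is up to 6 months, only the first 6 months of data for the mtDNA-PMM subjects" are kept. The same wording stands in SAP section 10.

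The event measures are crude. SAP 12.1 presents numbers and percentages of subjects with treatment-emergent AEs, overall and by period (to Day 28, Days 29 to 168, Days 169 to 336, later). SAP 12.2 counts subjects with at least one on-treatment PCI laboratory value. Under SAP 8.2, percentages use subjects with non-missing data in the analysis set. No person-time rate, Kaplan-Meier estimate or at-risk denominator is planned for events.

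On timing, SAP section 13 says of the interim CSR: "The data cut will be the date of the last subject last visit in REN001-201". SAP 3.3 says that "Protocol Version 2.0 extended recruitment to subjects with nDNA-PMM", so nDNA subjects were added after the study had been set up.

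**The concern.** An upper limit of 6 months on nDNA exposure describes the longest-followed subject. With rolling entry the others have less. Cutting the mtDNA data at that limit shortens one side and leaves nDNA subjects with partial follow-up in the denominator at full weight. Since the interim cut falls at the last REN001-201 visit, every set 1 subject has had the chance of 24 weeks on mavodelpar.

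A crude percentage counts a subject with three weeks of exposure and no event the same as one with 24 weeks and no event. The nDNA group would then show fewer events than set 1 for an administrative reason alone, which errs in the reassuring direction. Protocol 1.5 states that patients with nDNA mutations have no earlier REN001 exposure and that their safety profile is not expected to differ much from that of mtDNA patients. Protocol 1.3 says the nDNA data will support further development in that population. A spuriously low rate would bear directly on both.

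**Working it through.** The documents state no AE rate, no nDNA enrolment dates and no exposure distribution, so there is no planned figure to reproduce. What follows is an illustration.

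**Inputs from the documents.** Longest nDNA exposure 6 months, from the SAP 12 example; Month 6 is Day 168 (SAP 8.4). Set 1 opportunity 24 weeks = 168 days. Up to 50 nDNA subjects (SAP 3.5). Period boundaries Day 28 and Day 168 (SAP 12.1).

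**Assumptions.** The true risk p by Day 168 is the same in all groups. Set 1 is fully followed to Day 168. nDNA exposure at the cut is uniform over 0 to 168 days. The hazard is constant. Let H = -ln(1 - p); for p = 0.20, H = 0.2231.

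**1. Crude nDNA percentage against set 1.** Expected proportion = 1 - p/H = 1 - 0.20/0.2231 = 0.104. A true 20% shows as 10.4% (ratio 0.52). With 50 subjects, that is about 5 affected instead of 10. By the same formula, 10% shows as 5.1% and 50% as 27.9%.

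**2. Milder assumptions, p = 0.20.**

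- All nDNA exposure between 84 and 168 days: 1 - [exp(-H/2) - exp(-H)]/(H/2) = 1 - (0.8944 - 0.8000)/0.1116 = 0.154 (ratio 0.77).
- Front-loaded risk (Weibull, shape 0.5), exposure 0 to 168 days: 1 - (2/H²)[1 - (1 + H)exp(-H)] = 0.137 (ratio 0.69).

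**3. Against set 2.** These subjects count from the start of REN001-202 and are also partly followed at the cut. If their exposure were uniform over 0 to 336 days and capped at 168, half would be complete: 0.5 × 0.200 + 0.5 × 0.104 = 0.152. The nDNA/set 2 ratio would be 0.104/0.152 = 0.68. If their follow-up were as short as the nDNA group's, the ratio would be 1.0; if shorter, it would exceed 1.

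**4. The period split, p = 0.20, constant hazard, whole-set denominator.** Daily hazard h = 0.2231/168 = 0.001328.

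- To Day 28, set 1: 1 - exp(-28h) = 3.7%. nDNA: (28/168)[1 - 0.0365/0.0372] + (140/168)(0.0365) = 3.3%. Ratio 0.92.
- Days 29 to 168, set 1: 1 - exp(-140h) = 17.0%. nDNA: (140/168)[1 - 0.1697/0.1860] = 7.3%. Ratio 0.43.
- Dividing by subjects who enter the second period (140/168 of the nDNA group) gives 8.7%, ratio 0.52. That is better, but not a full correction within so long a period.

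**5. Person-time check.** First events per 168 days at risk. nDNA: 0.1037/0.4648 = 0.223. Set 1: 0.2000/0.8963 = 0.223. The ratio is 1.00, so under constant hazard the artefact goes.

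**6. Equal full follow-up.** Both groups show 20%; there is no distortion.

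**The case against.** The strongest reply is that nothing here is fixed. The same-site summaries may be presented, two sets may be used, exposure will be considered, and the 6-month cut is an example. All of it is descriptive, with no formal testing (SAP 8.1). A reader might infer that the SAP lays down a binding bridging rule; it does not. What remains is that this is the only method shown, and it does not do what matching is for.

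A reader might also infer that most nDNA subjects cannot have 6 months at the cut, or that the submission will contain a misleading bridging table. The documents give neither nDNA enrolment dates nor the date of the last REN001-201 visit, and do not assign the optional summary to the interim CSR. Nor do both mtDNA sets have the full period: that is assured only for set 1, apart from early discontinuations, and only up to about 24 weeks.

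The imbalance would be partly visible. Treatment duration is tabulated and kept at the interim (SAP 9.5), AEs are split by period, the first-month figures are little affected, and SAP 9.1 counts subjects with the potential to reach each visit. These displays signal unequal follow-up without correcting the event percentages, and the SAP 9.1 denominator applies only to attendance.

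Finally, although SAP section 10 repeats the wording ("Consideration will be given to the duration of exposure for nDNA-PMM subjects when summarising the data from the mtDNA-PMM subjects"), its by-visit summaries use subjects with data at the visit. This mechanism is not shown to affect them.

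**Conclusion.** The point holds for crude event summaries made while follow-up is incomplete: the interim, and the 120-day update if the comparison is repeated there. Matching on longest exposure leaves individual follow-up unequal, and no planned event measure allows for that.

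Against set 1, nDNA incidence would be biased low. In the illustrations at a true 20% it shows as 10.4% to 15.4%; these rest on assumed exposure patterns, hazards and risk, not on trial figures. Against set 2, neither direction nor size can be settled from the documents. At the final CSR, planned after all subjects have had the chance to complete (SAP section 13), the administrative imbalance largely disappears. The change is worth making because it is cheap and the bias against set 1 runs towards reassurance.

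**What to change.** In SAP section 12, for any nDNA/mtDNA event summary produced while follow-up is incomplete, specify for the nDNA group and each mtDNA set, over the same time span:

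1. Exposure-adjusted incidence: subjects with a first event divided by person-time at risk.
2. Kaplan-Meier cumulative incidence of first event, censored at withdrawal or data cut, with numbers at risk, read at the existing boundaries (Day 28, Day 168 and later) only where enough nDNA subjects remain at risk.
3. In the time-period AE split, the number of subjects entering each period as the denominator.

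Restricting crude percentages to subjects first dosed at least 168 days before the cut is not a good substitute. In the illustration it would leave almost no nDNA subjects: of 50, about 50 × 7/168 = 2 would have even 161 days. A Day 168 Kaplan-Meier reading would be nearly uninformative there too, hence the condition in item 2. At Day 28 about 50 × 140/168 = 42 would still be under follow-up, ignoring events and withdrawals.

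The cost is SAP wording, a little programming on dates already collected, and imprecise late estimates. The SAP section 10 by-visit summaries need no change.
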